3.2 Subject Sample

Subjects will be males and females aged 5 years of age and older. A total minimum of 105 subjects will be enrolled with 32-52 of those subjects being febrile. For the purpose of this testing, fever is defined as a core temperature of 99.5°F (37.5°C) or higher.

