3.2.2. Subject Qualification: Inclusion/ Exclusion Criteria

Inclusion Criteria

All subjects must meet the following inclusion criteria to be eligible for the study:

- Male or female.
- Age group: 5 years and up.
- Each subject or guardian must sign an informed consent form.

Exclusion Criteria

Subjects meeting any of the following criteria will be excluded from the study:

- Use of medications known to affect body temperature (for example, antipyretics, barbiturates, thyroid preparations, antipsychotics, etc.) within 3 hours of the test.
- immunization within seven days of the test.

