4.2 Primary Outcome Analysis

As per ISO 80601-2-56, these measures will be recorded and analyzed as follows:

1. *Clinical Accuracy* will be evaluated by comparing the first recorded measurement using the welloStationX with the single measurement recorded by the Welch Allyn SureTemp oral thermometer.

Results will be presented through:

- (i) Descriptive presentation of means and standard deviations
- (ii) Evaluation of agreement calculated as the clinical bias (mean bias (\pm SD))
- (iii) Limits of Agreement (LOA) calculations
- (iv) Band-Altman plot created using mean bias and standard deviation data
- (v) XY Plot and Correlation Coefficient calculation

2. Repeatability will be calculated using the pooled standard deviations formula.

All analyses will be performed and presented by febrile status (febrile and afebrile) and by device (test device compared with reference device), as applicable.

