6.2 Age

Table 2: Subject Age by Febrile Status

Age (years)	Febrile (n=33)	Afebrile (n=77)	Total (n=110)
Mean	44.91	44.73	44.78
Standard deviation	16.92	15.96	16.14

A **t-test for independent samples** revealed no statistically significant difference in mean age between febrile and afebrile subjects: $\mu_a - \mu_b = 0.18$; $t = +0.05$; $df = 108$; $p(\text{two-tailed}) = 0.96$ ($p > 0.05$).

Figure 1 below shows the age distribution of study subjects across the entire range.

[figure not shown]

Figure 1. Age distribution of study subjects.

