7.2 Clinical Bias

Agreement through clinical bias evaluation was calculated as the Mean Bias \pm SD by subtracting the first output measurement recorded with the welloStationX thermometer (DUT) from the corresponding output measurement recorded with the Welch Allyn SureTemp oral thermometer for each subject, and then calculating the Mean Bias \pm SD of the biases.

Table 5 below shows clinical bias by febrile status.

Table 5: Clinical bias by febrile status.

Mean bias \pm SD Febrile (n=33)	Mean bias \pm SD Afebrile (n=77)	Mean bias \pm SD All (n=110)
0.25 °F \pm 0.33	-0.06 °F \pm 0.42	0.03 °F \pm 0.42

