7.4 XY Plot and Correlation Coefficient

To further demonstrate the closeness of the relationship between the welloStationX (DUT) and the SureTemp (reference) readings, an XY plot of the two sets of readings was created and is shown in Figure 3 below.

[figure not shown]

Figure 3: XY Plot of welloStationX versus SureTemp for all subjects

$R^2 = 0.80$, indicating a strong linear relationship

8. Clinical Repeatability

Clinical Repeatability was calculated using the pooled standard deviations of the triplicate measurements recorded by the welloStationX.

Table 5 below shows clinical repeatability by febrile status.

Table 5: Clinical repeatability of the welloStationX by febrile status.

Febrile (n=33)	Afebrile (n=77)	All (n=110)
0.13	0.09	0.06

9. Safety Evaluation

There were no observed or reported adverse events for any subject in the study.

DISCUSSION

The results of this clinical study are interpreted both with respect to the study dataset alone and compared to the research data published in the following whitepaper:

Clinical validation of the CAREGIVER® non-contact thermometer model PRO-TF200/PRO-TF300 in febrile and afebrile patients of all ages

Naja E. [name], Alice Huang & Gary O'Hara MSE

November 2013 Copyright ©2013 Thermomedics®, Inc.

This comparison was selected for the following reasons:

1. The reported study clinical data was that which was submitted to the FDA in support of market clearance for the Caregiver Professional Clinical Thermometer (K131771) which is the predicate device in the current submission for K180298.
2. In the reported study, the reference thermometer used was the Welch Allyn SureTemp oral thermometer, the same reference thermometer used in the welloStationX clinical precision study.

There were no notable differences in gender, age or ethnicity by febrile status and age distributions across the spectrum was well represented. Therefore, the subject population was across febrile status was homogenous and the sample overall representative of the intended patient population.

The limits of agreement for the welloStationX are (+0.86, -0.80) which is better than that for the Caregiver study whose limits of agreement was (+0.82, -1.21).

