The intent of this study was to clinically validate application of the welloStationX automated no-contact thermometer to the reference device, the Welch Allyn SureTemp oral thermometer. The validation results indicate a high level of agreement between the welloStationX and the SureTemp. Repeatability across three sequential measurements with the welloStationX indicated high precision. It can be concluded that the welloStationX automated non-contact thermometer is an accurate and reliable tool to measure body temperature of individuals five years of age and older.

END OF DOCUMENT

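### The report concludes accuracy from age five upward, but no accuracy or repeatability result by age is planned or reported

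*SAP*

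**What the plan says.** **Eligibility and sample.** Protocol section 3.2.2 takes one age band: "Age group: 5 years and up". Section 3.2 sets the size and a single quota, on febrile status: "A total minimum of 105 subjects will be enrolled with 32-52 of those subjects being febrile". Nothing is set for age.

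**Planned analysis.** Protocol section 3.3.1 records age for each subject. Section 4.2 then fixes the breakdown: "All analyses will be performed and presented by febrile status (febrile and afebrile) and by device (test device compared with reference device), as applicable". Age is not in that list.

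**Reported analysis.** Report section 7.1 gives means and SDs by febrile status. Section 7.2 does the same for bias, adding an overall column ("Table 5 below shows clinical bias by febrile status"), and section 8 follows that pattern for repeatability. Section 7.3 gives one pair of limits of agreement (+0.86, -0.80) and section 7.4 one R² (0.80), both for all subjects.

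**What is said about age.** Section 6.2 has "Table 2: Subject Age by Febrile Status", a t-test of mean age between febrile and afebrile subjects (p = 0.96), and Figure 1. The Discussion says "age distributions across the spectrum was well represented" and from this, with the similarity by febrile status, infers that the sample represents the intended population. The Conclusion states that the device "is an accurate and reliable tool to measure body temperature of individuals five years of age and older".

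**The concern.** The indication in Protocol section 1.2 starts at age five, and the Conclusion repeats that lower limit. The device converts forehead skin temperature to an oral equivalent (Protocol section 2.0), and no reported result looks at that conversion in children separately. The stated objective is bias with its uncertainty, yet no bias or uncertainty is given for anyone below adult age.

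The t-test in section 6.2 does not fill the gap. It compares the mean age of febrile and afebrile subjects. Two groups can have the same mean age with hardly any children in either, and equal mean ages say nothing about accuracy at a given age.

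At stake is the lower end of the age claim. The adult part is not in question here.

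**Working it through.** **Step 1. Reproduce the age table.** Inputs from report Table 2: febrile n = 33, mean 44.91, SD 16.92; afebrile n = 77, mean 44.73, SD 15.96.

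- Combined mean = (33 × 44.91 + 77 × 44.73)/110 = 44.784 (stated 44.78).
- Combined SD = √[(32 × 16.92² + 76 × 15.96² + (33 × 77/110) × 0.18²)/109] = 16.18 (stated 16.14, a 0.2% difference).
- t = 0.18/[16.25 × √(1/33 + 1/77)] = 0.053, p = 0.958 (stated 0.05 and 0.96).

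The table reproduces. The text states no number of children, so none can be reproduced.

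**Step 2. How many subjects under 18 fit mean 44.78, SD 16.14, n = 110?** The distance to 18 in SD units is (44.78 − 18)/16.14 = 1.66.

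| Assumption about the age distribution | Under 18 |
|---|---|
| Normal: 110 × Φ(−1.66) | 5.3 |
| Normal truncated at 5, same mean and SD | 5.3 |
| Uniform, same mean and SD | 2.3 |
| Gamma starting at 5, same mean and SD | 1.6 |
| Any unimodal shape: 110 × (4/9)/(1 + 1.66²) | at most about 13 |
| Any shape at all: 110 × 1/(1 + 1.66²) | at most about 29 |

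The last bound needs an artificial two-point distribution; with the children all aged 17 it is 27.

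**Step 3. Precision in a subgroup of k children.** Assume children share the overall SD of paired differences, 0.42°F (report section 7.2). The 95% half-width for bias is t(0.975, k−1) × 0.42/√k. For each limit of agreement it is t × 0.42 × √[1/k + 1.96²/(2(k−1))].

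- k = 5: bias 2.776 × 0.42/√5 = 0.52°F; each limit 0.96°F.
- k = 13: bias 2.179 × 0.42/√13 = 0.25°F.
- k = 29: bias 2.048 × 0.42/√29 = 0.16°F; each limit 0.28°F.
- All 110: bias 1.982 × 0.42/√110 = 0.08°F.

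With 5 children, the uncertainty on each limit (0.96°F) exceeds the reported limits themselves (+0.86, -0.80).

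**Step 4. Would the pooled bias reveal a difference in children?** If k of 110 subjects had a bias differing by d from the rest, the overall mean would move by (k/110) × d. Take d = 0.5°F as an illustration: 5 children move it by 0.02°F and 13 by 0.06°F, both inside ±0.08°F. Twenty-nine would move it by 0.13°F, but nothing in the report would tie that shift to age.

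**The case against.** The best defence is that the protocol treats five and up as one group and sizes the study on that basis. The standard, as quoted in Protocol section 3.2.1, asks for at least 105 subjects with 30% to 50% febrile in the selected age group. The report has 110 subjects, 33 of them febrile (30%). Nothing in the documents requires results by age band, and the 5-17 and 18-and-over split is a reviewer's choice. All of this stands. It explains why there is no split, but it is not evidence of accuracy in children.

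Second, Figure 1 is cited as showing the age distribution and may well show how many children took part. Its absence from the extracted text is not a fault in the report, and the Discussion's statement on age coverage may rest on it. That also stands, so the number of children here is an inference. Even a full age histogram, however, gives no bias or repeatability by age.

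Third, with about 5 children an age table would neither support nor refute accuracy in them. That is true, and the Conclusion should then say so.

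A reader might go further and infer that the result is purely an adult one, or that the device is inaccurate in children. The documents support neither. Mean and SD allow anything up to about 29 subjects under 18, at which point the subgroup estimate would be usable. No data in the documents show that bias varies with age.

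**Conclusion.** The concern holds as a gap between the conclusion and the results. The plan followed as written produces no accuracy or repeatability result by age, and the report's comparison of mean ages does not supply one.

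How much this matters depends on a count that the available text does not give. At 2 to 5 children, the figure for ordinary smooth age distributions, the data could say almost nothing about children alone. At 13 the bias would be known to about ±0.25°F, and at 29 to ±0.16°F. These figures rest on two assumptions: that the mean and SD in Table 2 are a fair guide to the number of children, and that the SD of 0.42°F applies to them.

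This should be corrected before the age claim is relied on. It does not undermine the pooled result.

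**What to change.** In report section 7, add one table, labelled post hoc and descriptive, for ages 5-17 and 18 and over. It should give n, mean bias with 95% confidence interval, limits of agreement and repeatability, split by febrile status only where numbers allow.

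In the Discussion, replace the general statement on age coverage with the counts by age band.

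Word the Conclusion to match the table. If few children were enrolled, state that accuracy in the 5-17 group was not separately established.

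The report is the place for this. Data collection ended in October 2018, so adding the split to Protocol section 4.2 now would not make it prespecified.

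The cost is one table from data already collected, with no new enrolment. The downside is a narrower conclusion if the 5-17 group proves small.
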